**6.3.1.4. PK Concentrations**

*Serum concentrations for PF-06252616 will be listed and summarized descriptively by nominal PK sampling time and dose. Individual subject and median profiles of the serum concentration time data will be plotted.*

To assess the PK profile of PF-06252616, PK concentrations will be listed, summarized and plotted for subjects in the PK analysis set, where missing and BLQ values will be handled as detailed in [Section 6.3.1.1](#).

Presentations for PF-06252616 will include:

- A listing of all concentrations sorted by dose, subject ID, period, Visit, and nominal time postdose. The listing of concentrations will include the actual time postdose. Deviations from the nominal time will be given in a separate listing.
- A summary of concentrations by dose, period, sequence, Visit, and nominal time postdose, where the set of statistics will include n, mean, median, standard deviation, coefficient of variation (cv), minimum, maximum and the number of concentrations above the lower limit of quantification. Two concentration summaries will be provided: one for all subjects, and one for the subjects with additional PK sampling.
- Median concentrations against nominal time postdose by Period, Sequence and Dose (there will be separate plots for each 16-week dose escalation within a Period). Linear scale.
- Mean concentrations against nominal time postdose by Period, Sequence and Dose (there will be separate plots for each 16-week dose escalation within a Period). Linear scale.
- Individual concentrations against actual time postdose by Period, Sequence and Dose (separate plots for each 16-week dose escalation within a Period, including all subjects). Linear scale.
- Median concentrations against nominal time postdose by Period, Sequence and Dose. There will be one page per 48-week Period with all sequences on the same plot. Linear scale.

090177e1909dd632\Approved\Approved On: 25-Mar-2019 05:54 (GMT)

- Median trough (predose) concentrations against nominal dosing week by Period, Sequence and Dose. There will be one plot per 48-week Period with all Sequences on the same page; Individual subject trough concentrations will also be plotted by Period and Sequence (separate plot for each 16 week dose escalation within a Period, including all subjects). Linear scale.
- Median concentrations at the end of infusion (nominally at 2 hour post start of infusion) against nominal dosing week by Period, Sequence and Dose, as described above for trough concentrations. Individual subject end of infusion concentrations will also be plotted. Linear scale.
- For Sequence 2, Period 2 only (placebo treatment, assessing terminal phase concentrations following active treatment in Period 1), median concentrations will be plotted against nominal time on a semi-log scale. Individual subject concentrations will also be plotted against actual time (all subjects on the same page). Nominal and actual time for these plots will be defined as weeks after the last dose of Period 1 (Week 48).

The range for the x-axes of these plots will be decided on review of the data, and will depend on how long PF-06252616 concentration is quantifiable in the matrix.

For summary statistics and median plots by sampling time, the nominal PK sampling time will be used. For individual subject plots by time, the actual PK sampling time will be used.

### **6.3.2. Pharmacodynamic Analysis**

#### **6.3.2.1. Deviations, Missing Concentrations and Anomalous Values**

In summary tables and plots of the median values at each time point, statistics will be calculated having set concentrations to missing if 1 of the following cases is true:

1. A concentration has been collected as ND (ie not done) or NS (ie no sample).
2. A deviation in sampling time is of sufficient concern.

#### **6.3.2.2. GDF-8 Parameters**

If a GDF-8 parameter cannot be derived from a subject's concentration data, the parameter will be coded as NC (ie not calculated). (Note that NC values will not be generated beyond the day that a subject discontinues).

In summary tables, statistics will be calculated by setting NC values to missing; and statistics will not be presented for a particular treatment if more than 50% of the data are NC. For statistical analyses (ie analysis of variance), GDF-8 parameters coded as NC will also be set to missing.

To assess the relationship between the GDF-8 trough concentrations and dose,  $C_{\text{trough(GDF-8)}}$  after last dose at each dose level will be plotted against dose, and will include individual subject values and the medians for each dose level. Medians will have a different symbol

than the individual values. A footnote will be added to the plots to indicate that medians are presented on the plot.

$C_{\text{trough(GDF-8)}}$  for the last dose of each dose escalation level will be summarized for Process 1 and Process 2 material as described above for PK.

### 6.3.2.3. GDF-8 Concentration

*Graphical analysis of total GDF-8 levels as absolute and change from baseline will be performed.*

To assess the PD profile of PF-06252616, GDF-8 concentrations will be listed, summarized and plotted for subjects in the PD analysis set, where missing the data will be handled as outlined in [Section 5.3](#).

- A listing of all concentrations (observed values, and change from baseline) sorted by dose, subject ID, period, Visit, and nominal time postdose. The listing of concentrations will include the actual sample times. A summary of concentrations by dose, period, Visit, sequence and nominal time postdose, where the set of statistics will include n, mean, median, standard deviation, coefficient of variation (cv), minimum, maximum and the number of concentrations above the lower limit of quantification.
- Median total GDF-8 concentrations and Change from Baseline against nominal time postdose by Period, Sequence and Dose (there will be separate pages for each 16-week dose escalation within a Period). Linear scale.
- Mean total GDF-8 concentrations and Change from Baseline against nominal time postdose by Period, Sequence and Dose (there will be separate pages for each 16-week dose escalation within a Period). Linear scale.
- Individual total GDF-8 concentrations and Change from Baseline against actual time postdose by Period, Sequence and Dose (separate pages for each 16-week dose escalation within a Period, including all subjects). Linear scale.
- Median total GDF-8 concentrations and Change from Baseline against nominal time postdose by Period, Sequence and Dose. There will be one plot per 48-week Period with all sequences on the same page; for Sequence 1 in Period 2 (maximum tolerated dose) there will be a separate line for each dose. Linear scale.

The range for the x-axes of these plots will be decided on review of the data, and will depend on how long GDF-8 concentration is quantifiable in the matrix.

For summary statistics and median plots by sampling time, the nominal GDF-8 sampling time will be used. For individual subject plots by time, the actual GDF-8 sampling time will be used.

### 6.3.3. Additional MRI Analysis

For the additional MRI endpoints of change from baseline in Whole Thigh Mean Fat Fraction, Mean T2 relaxation time, Percent Probable Muscle and Percent Probable Fat (defined in [Section 3.3.3](#)), similar analyses as described in [Section 6.2](#) for the Whole Thigh Muscle Volume and Whole Thigh Muscle Volume Index will be conducted, including the evaluations of their predictive relationship to the primary endpoint 4SC time.

### 6.4. Subset Analyses

In the pre-specified subset of subjects who have baseline 4SC <3.5 seconds, ≥3.5 seconds and ≤8 seconds, or >8 seconds (see [Section 3.2](#)), the mean change from baseline as compared to placebo on muscle strength by myometry and on function tests including, 4SC, FVC, NSAA, PUL, 6MWD at Week 17, 33 and 49, will be analyzed using the methods as described in [Section 6.1](#) and [6.2](#). Similar subsets will also be analyzed for changes from baseline as compared to placebo on MRI endpoints at Week 17, 33, 49 as described in [Section 6.2](#) and [6.3](#).

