#### 2.1.2. Secondary

- To characterize the effects of PF-06252616 on muscle strength and other functional assessments compared to placebo.
- To evaluate the PD activity of PF-06252616 based on the percent change of muscle volume from baseline as compared to placebo.
- To evaluate the PD profile of PF-06252616 based on GDF-8 (myostatin) modulation in blood.
- To characterize the PK profile of PF-06252616.
- To evaluate the immunogenicity of PF-06252616.
- To characterize the long-term effects following approximately 2-years of treatment with PF-06252616 on functional assessments compared to historical control.
- To characterize the effects of PF-06252616 on muscle strength and functional assessments compared to placebo in subset of subjects who may demonstrate a rapid disease decline and with relatively low variability over a one-year period.

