### **2.2.3. Secondary Endpoints-Based on Data from Period 1 and 2**

#### **2.2.3.1. Strength and Function**

- Mean change from baseline as compared to placebo on function tests including, Forced Vital Capacity (FVC), Northstar Ambulatory Assessment (NSAA), range of motion (ROM), Performance of Upper Limb (PUL), 6MWD at Week 17, 33 and 49. Mean change from baseline as compared to placebo on the 4 SC at Week 17 and 33.

- Mean change from baseline as compared to placebo on muscle strength by myometry at Week 17, 33 and 49.
- In subject randomized to Sequence 1, mean change from baseline as compared to historical control on functional tests including, 4SC, 6MWD, FVC, NSAA at Week 97.
- In a pre-specified subset of subjects who may demonstrate a rapid disease decline and with relatively low variability, the mean change from baseline as compared to placebo on function tests including, 4SC, FVC, NSAA, PUL, 6MWD at Week 17, 33 and 49. The definition of this subgroup will be detailed in the Statistical Analysis Plan (SAP).
- In a pre-specified subset of subjects who may demonstrate a rapid disease decline, the mean change from baseline as compared to placebo on muscle strength at Week 17, 33 and 49.

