	definition of the subset).	
Because the placebo arm in the study is only for 1 year (during period 1 in Sequence group 3) the plan is to review the functional data as compared to a matched historical control group.
 
 
The second objective will allow for an analysis in a subset of subjects who may be more likely to decline in one-year who also may have less variability, as determined by their baseline data. This subset is being proposed following a review of additional natural history data which was not available at the time of the initial study design. As additional natural history data are obtained 4SC baseline values which predict patients who are more likely to decline in one year with less variability will be evaluated.
 

2	In CCI the decision boundaries for the interim analysis have been updated.	
 
CCI
 

2	
In Section 3.2 and Section 6.2:
 
Endpoints were updated to describe the data that will be used to evaluate the two new secondary objectives.
 
Corrections were made to time points for endpoints.
 
Removed strength testing by Medical Research Council (MRC) Scale to reduce the burden of testing on subjects.
	Reflect the corresponding changes made in the revised protocol.
2	In Section 5.3 , added additional sensitivity analyses.	Resulted from discussions with regulatory authorities.

090177e1909dd632\Approved\Approved On: 25-Mar-2019 05:54 (GMT)

2	In Section 3.3.1, 3.3.2, 6.3.1, and 6.3.2, updated PK and PD endpoints and analysis.	Based on planned PK/PD data collection schedule and data availability.
2	In Section 6.4, added a subset analysis.	Reflect the changes made in the revised protocol.
3	In Section 7.1 and CCI	Reflect the changes in the interim analysis decision criteria.
4	In CCI	CCI
5	In Section 3.2, 3.3, 6.2, and 6.4.	Clarified endpoint details including the pre-specified subsets, the timed function tests within the NSAA endpoint, and the PODCI score.
5	In Section 3.5.	Clarified the AE Tier-2 event definition to align with the “Rule of 4” given the trial will have less than 400 or fewer subjects per treatment group, and clarified the AE Tier-3 event analysis.

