### 2.1.2. Secondary

- **S1:** To characterize the effects of PF-06252616 on muscle strength and other functional assessments compared to placebo.
- **S2:** To evaluate the PD activity of PF-06252616 based on the percent change of muscle volume from baseline as compared to placebo.
- **S3:** To evaluate the PD profile of PF-06252616 based on GDF-8 (myostatin) modulation in blood.
- **S4:** To characterize the PK profile of PF-06252616.
- **S5:** To evaluate the immunogenicity of PF-06252616.
- **S6:** To characterize the long-term effects following approximately 2-years of treatment with PF-06252616 on functional assessments compared to historical control (see [Section 6.2.1](#)).
- **S7:** To characterize the effects of PF-06252616 on muscle strength and functional assessments compared to placebo in a subset of subjects who may demonstrate a rapid disease decline and with relatively low variability over a one-year period (see [Section 6.4](#)).

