#### 3.2. Secondary Endpoints

- *Mean change from baseline as compared to placebo on function tests including, Forced Vital Capacity (FVC), Northstar Ambulatory Assessment (NSAA), range of motion (ROM), Performance of Upper Limb (PUL), 6MWD at Week 17, 33, and 49.*
- *Mean change from baseline as compared to placebo on the 4SC at Week 17 and 33.*
- *Mean change from baseline as compared to placebo on muscle strength by myometry at Week 17, 33, and 49.*
- *In subjects randomized to Sequence 1, mean change from baseline as compared to historical control (see [Section 6.2.1](#)) on functional tests including, 4SC, 6MWD, FVC, NSAA at week 97.*
- *In the pre-specified subset of subjects who have baseline 4SC <3.5 seconds, ≥3.5 seconds and ≤8 seconds, or >8 seconds, the mean change from baseline as compared to placebo on muscle strength by myometry and on function tests including, 4SC, FVC, NSAA, PUL, 6MWD at Week 17, 33 and 49.*

Within the Northstar Ambulatory Assessment (NSAA), the two timed function tests, Rise from Floor and Run 10 meters will be analyzed separately for summary tabulation along with the total NSAA score.

The forced vital capacity(FVC) has been collected as the best 3 values at each of the given visits. Only the single best value (maximum forced vital capacity) will be used to analyze the FVC assessment. The percent predicted FVC is provided on the case report form from the best FVC value.

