## 5. GENERAL METHODOLOGY AND CONVENTIONS

### 5.1. Hypotheses and Decision Rules

The assumed null and alternative hypotheses for testing the active treatment versus the placebo on the 4 stair climb are included below:

$$H_0: (\mu_{\text{active, 49 weeks}} - \mu_{\text{active, baseline}}) - (\mu_{\text{placebo, 49 weeks}} - \mu_{\text{placebo, baseline}}) = 0$$

$$H_1: (\mu_{\text{active, 49 weeks}} - \mu_{\text{active, baseline}}) - (\mu_{\text{placebo, 49 weeks}} - \mu_{\text{placebo, baseline}}) > 0$$

The primary efficacy analysis will be tested at  $\alpha=0.025$  (one-sided). The same type 1 error rate will be used for testing the secondary analyses. This test will be performed based on the data in period 1 from all subjects. Subjects assigned to sequence 1 and sequence 2 will be analyzed together in an active treatment group compared to subjects in sequence 3 (placebo during period 1).

The decision criteria for the interim analysis is described in CCI

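### Objective S7 promises one rapid-decline, low-variability subset, but the SAP gives three baseline 4SC bands that include every boy and does not say which band answers S7

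*SAP*

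**What the plan says.** Protocol 2.1.2 states the objective as effects against placebo "in subset of subjects who may demonstrate a rapid disease decline and with relatively low variability over a one-year period". SAP 2.1.2 repeats it as S7, "in a subset of subjects who may demonstrate a rapid disease decline and with relatively low variability over a one-year period", and refers the reader to SAP 6.4. Protocol 2.2.3.1 calls the subset pre-specified and defers the details: "The definition of this subgroup will be detailed in the Statistical Analysis Plan (SAP".

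SAP 6.4 then gives: "In the pre-specified subset of subjects who have baseline 4SC <3.5 seconds, ≥3.5 seconds and ≤8 seconds, or >8 seconds". SAP 3.2 uses the same bands, "subjects who have baseline 4SC <3.5 seconds, ≥3.5 seconds and ≤8 seconds, or >8 seconds", and SAP 6.2 repeats them. None of the three sections links a band to rapid decline or to low variability.

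The SAP version history shows how the subset developed. The version 2 rationale says that "4SC baseline values which predict patients who are more likely to decline in one year with less variability will be evaluated", so the choice was still open then. The version 5 entry reads "Clarified endpoint details including the pre-specified subsets", in the plural.

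On error rates, SAP 5.1 tests the primary endpoint at one-sided 0.025 and adds: "The same type 1 error rate will be used for testing the secondary analyses". The readable text gives no multiplicity rule for the secondary efficacy analyses.

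**The concern.** S7 was written for a group chosen on two properties, fast decline and low variability, in which a drug effect might be easier to see. A definition that includes every boy selects no such group. The analyses can still be run, but the plan does not say in advance which one answers S7.

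The stake is how a subgroup result is read. If one band shows a benefit and the other two do not, the favourable band can be reported as the pre-specified S7 finding, because the SAP describes all three under that term. A reader of the study report could not tell a planned choice from one made after seeing the data.

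**Working it through.** **1. The plan's own figure.** No sample size, power or error rate is stated for S7. The nearest figure is the primary sample size in Protocol 9.1: difference 2.5 s, SD 4.0, 80% power, two-sided 0.05, 2:1 allocation, one interim analysis, 96 completers. Without an interim, the placebo arm needs 1.5 × [4.0 × (1.960 + 0.842) / 2.5]² = 30.1, so the total is 3 × 30.14 = 90.4. An efficacy boundary from the gamma family with γ = −1 at 50% information inflates this by 1.052, to 95.1, or 96 when rounded to 2:1. The figure is reproduced.

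**2. Do the bands cover everyone?** Eligibility at screening is 0.33 to 1.6 stairs per second (Protocol 4.1), which is 4/1.6 = 2.5 s to 4/0.33 = 12.1 s. A baseline time may differ from the screening time, but the lowest and highest bands are open-ended, and the cuts at 3.5 s and 8 s leave no gap or overlap. Protocol 6.2 requires a baseline 4SC at randomization. Each randomized boy therefore falls in exactly one band, and the union is the whole trial.

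**3. False-positive chance per outcome and visit.** The bands contain different boys, so the three tests can be treated as independent. With each at one-sided 0.025 (SAP 5.1):

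- one named band: 0.025
- any of three bands: 1 − (1 − 0.025)³ = 1 − 0.9269 = 0.0731
- Bonferroni across three bands: 0.025/3 = 0.0083 per band

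**4. What this does not count.** SAP 6.4 lists strength plus five function tests at three visits, so there are 6 × 3 = 18 comparisons per band and 54 across the three, before the MRI endpoints. The 18 would remain if one band were named. Only the factor of three comes from this defect, and 7.3% against 2.5% measures it for each outcome and visit.

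**5. Precision within a band.** The documents give no band sizes, so these are assumptions. With N completers at 2:1, the standard error is 4.0 × √(4.5/N). For a true difference of 2.5 s at one-sided 0.025, power is:

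| Assumed completers in the band | Standard error (s) | Power |
|---|---|---|
| 24 | 1.73 | 30% |
| 32 | 1.50 | 38% |
| 48 | 1.22 | 53% |

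This uses the trial-wide SD. S7 presumes a smaller SD in its subset, but the documents give none by band.

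**The case against.** The best defence is that three ordinary subgroup analyses were intended. The plural in the version 5 log and a plural reference in SAP 6.4 support this, and one cut is the 8 s stratification boundary. The cut-points are fixed and the SAP commits to analysing all three bands, so no band can be quietly dropped. S7 aims only to characterise effects, it is a secondary objective of a Phase 2 trial, and the readable SAP controls familywise error for no secondary endpoint.

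Most of this stands. A reader might infer that S7 cannot be analysed at all, or that its analysis merely repeats the whole-trial one. The documents do not support either reading, because band-by-band results will exist and can inform S7. A reader might also infer that unfavourable bands could be withheld, but the commitment to analyse all three leaves selective emphasis as the risk. The defence does not supply the missing link between a band and the two properties named in S7.

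Two further inferences fail. One is that the documents themselves identify 3.5 to 8 s as the S7 band. Their only prognostic statement about a band, in Protocol 1.10, is that times above 8 s are associated with loss of ambulation within 12 months, which on its face suggests faster decline there. The other is that S7 was added because one-year change proved smaller than first estimated (0.9 to 1.99 s against about 2.9 s). The SAP version history gives that as the reason for S6, the historical-control objective. For S7 it cites boys more likely to decline and possibly less variable.

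**Conclusion.** The concern holds in a limited form. The protocol promised one defined subset. The SAP provides a division of the whole trial, and no readable text says which part answers S7. The size is a 7.3% chance of at least one false-positive band per outcome and visit, against 2.5% for one named band. This rests on three independent tests at one-sided 0.025, on no effect in any band, and on a willingness to present any favourable band as the S7 result.

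A reader might infer that the trial's main error rate is affected. It is not, because the primary test uses all subjects and does not depend on the bands.

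One limit remains. The SAP version history mentions a baseline requirement for a subgroup in the second tier of the interim decision, and its details are blacked out. That subgroup may match one of the bands, but this cannot be checked. S7 refers to SAP 6.4, which is readable, so the redaction does not supply the missing definition.

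**What to change.** In SAP 3.2, 6.2 and 6.4, before unblinding, name the single baseline 4SC band that is the S7 subset, cite the natural-history evidence for faster decline and lower variability in it, and label the other two bands as descriptive subgroups. If no band can be justified, label all three as descriptive, or apply a multiplicity rule across them, for example 0.0083 one-sided per band.

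The 3.5 to 8 s band is a plausible candidate. Times above 8 s are linked to loss of ambulation, and the protocol stops collecting the 4SC in boys who become non-ambulatory, so that band would tend to lose 4SC data. This is an inference that the sponsor must confirm from its own natural-history data.

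The cost is SAP wording. All three sets of tables can still be produced and no new data are needed. The sponsor gives up the option of claiming S7 from another band.

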### 6.5. Baseline and Other Summaries and Analyses

At baseline, Subjects will be stratified into two groups based on their ability to complete the 4SC in ≤8 seconds or >8 second. This stratification factor may be used as a covariate in the statistical model when modeling data besides the 4 stair climb.

